**Table 6-3 Dose reduction steps for capmatinib**

Capmatinib dose levels	Capmatinib daily dose
Starting dose level	400 mg BID (= 2 x 200 mg tablets twice in a day; 800 mg total daily dose)
Dose level -1	300 mg BID (= 2 x 150 mg tablets twice in a day; 600 mg total daily dose)
Dose level -2	200 mg BID (= 1 x 200 mg tablets twice in a day; 400 mg total daily dose)

**Table 6-4 Dose reduction steps for ribociclib**

Ribociclib dose levels	Ribociclib daily dose
Starting dose level	600 mg QD (= 3 x 200 mg tablets once in a day; 600 mg total daily dose)
Dose level -1	400 mg QD (= 2 x 200 mg tablets once in a day; 400 mg total daily dose)
Dose level -2	200 mg QD (= 1 x 200 mg tablets once in a day; 200 mg total daily dose)

### 6.3.1.2 Maximum duration of study drug(s) interruption

If the treatment with spartalizumab is interrupted for more than 12 weeks (counted from the time the AE reaches a grade that leads to spartalizumab interruption), spartalizumab must be permanently discontinued.

If the treatment with LAG525 is interrupted for more than 12 weeks (counted from the time the AE reaches a grade that leads to LAG525 interruption), LAG525 must be permanently discontinued.

If the treatment with capmatinib is interrupted for more than 3 consecutive weeks (counting from the first day when a dose was interrupted), then capmatinib must be permanently discontinued.

If the treatment with ribociclib is interrupted for more than 28 consecutive days due to ribociclib-related toxicity (counting from the first day when a dose was interrupted, including the 7 days of planned interruption of dosing between Day 22-28 of a cycle), then ribociclib must be permanently discontinued.

If the treatment with canakinumab is interrupted for more than 4 weeks (counted from the intended day of the next scheduled dose), canakinumab must be permanently discontinued.

### 6.3.1.3 Mandatory dose modification for spartalizumab and LAG525

No changes in dose of spartalizumab and LAG525 are allowed. Overall, subjects with AE suspected to be related to spartalizumab and LAG525 including those of potential immune-mediated etiology (irAEs) may need to interrupt or permanently discontinue spartalizumab or/and LAG525 as outlined below, in [Section 6.3.1.3.2](#) and in [Table 6-5](#) to [Table 6-12](#) or as listed in [Section 7.1.5](#).

In general, spartalizumab or/and LAG525 must be permanently discontinued in case of:

- Any life-threatening adverse reactions (excluding endocrinopathies controlled with hormone replacement therapy)
- Persistent grade 2 or 3 adverse reactions (excluding endocrinopathies controlled with hormone replacement therapy) that do not recover to  $\leq$  Grade 1 within 12 weeks
- Inability to reduce the dose of steroids (for the management of irAEs) to  $\leq$  10 mg/day prednisone or equivalent within 12 weeks.
- Any severe or grade 3 recurring treatment-related adverse reaction
- Any grade 4 irAE

Note: the 12 week timeframe will begin from the time the irAE reaches a Grade that leads to spartalizumab/LAG525 interruption.

#### 6.3.1.3.1 Guidance for corticosteroids tapering for management of immune-related AEs

Steroids should be tapered slowly and based on response/recovery of clinical symptoms. Consider to complete tapering over a period of at least 4 weeks. Slower tapering of corticosteroids therapy may be recommended if the adverse event is not showing improvement. If dose level of  $\leq$  10 mg of prednisone (or equivalent) is achieved, spartalizumab or/and LAG525 can be restarted as indicated in [Table 6-5](#) to [Table 6-12](#).

### 6.3.1.3.2 Dose modification for potential immune-mediated adverse events (irAEs)

Adverse events of special interest include irAEs that are associated with spartalizumab/LAG525 treatment. An irAE may be experienced by subjects treated with spartalizumab or/and LAG525 due to their mechanism of action and predicted based on the reported experience with other checkpoint inhibitors that have a similar mechanism of action. Investigators must be vigilant and carefully identify AEs that may be suggestive of potential irAEs as their appearance may be sub-clinical and early diagnosis is critical for adequate management and resolution.

Immune-related adverse events may be of low grade and self-limited, most frequently involving the gastrointestinal tract (e.g. diarrhea/colitis), skin (e.g. rashes, pruritus), liver (e.g. hepatitis), lung (e.g. pneumonitis), kidneys (e.g. nephritis) and endocrine systems (e.g. hypothyroidism, hyperthyroidism, type I diabetes, hypophysitis including hypopituitarism and adrenal insufficiency). Other immune-related AEs may rarely include the nervous system (e.g. encephalitis, Guillain-Barre syndrome, myasthenia gravis), eye (e.g. uveitis, vision changes), musculo-skeletal system (e.g. myositis, arthritis), pancreas (e.g. pancreatitis), cardio-vascular system (e.g. vasculitis, myocarditis) or blood system (e.g. anemia, cytopenias), and severe skin reactions such as toxic epidermal necrolysis or Stevens-Johnson syndrome. Furthermore, complications in patients with bone marrow or solid organ transplant have been reported (e.g. organ rejection, severe graft-versus-host disease). However, nearly all organs can be affected by immune-mediated toxicities. IrAEs often occur relatively early (mostly within weeks to 3 months after treatment initiation), however, may develop at any time during treatment (even after several months), and may also occur after treatment discontinuation. Serological, immunological and histological assessments should be performed as deemed appropriate by the investigator, to verify the potential immune-mediated nature of the AE, and exclude neoplastic, infectious or metabolic origin of the AE.

Severe grade or persistent lower grade irAEs typically require treatment interruption or permanent discontinuation of treatment and administration of systemic steroids, and sometimes other immunosuppressive medications (i.e. TNF $\alpha$  antagonists, mycophenolate or tacrolimus, etc.). Early recognition and work-up of irAEs and initiation of treatment are critical to reduce the risk of complications, since the majority of irAEs are reversible with the use of steroids and other immune suppressants. Some events like endocrinopathies may require life-long hormonal replacement. Tapering of steroids should not be too rapid to avoid recurrence or worsening of irAE (Section 6.3.1.3.1). The management of irAEs may further include initiation of antibiotics for prophylaxis against opportunistic infections.

Subjects should be instructed to return to the study site as soon as possible (instead of waiting for their next scheduled visit) if they experience symptoms consistent with an irAE. Subjects who experience a new or worsening irAE should be contacted and/or evaluated by the study site more frequently as applicable.

**Table 6-5 Colitis/diarrhea suspected to be related to spartalizumab or spartalizumab/LAG525**

Grade (CTCAE v5)	Mandatory dose modification
Grade 2	If diarrhea is grade 2, despite loperamide at 2 mg every 2 hours for > 48h: Interrupt spartalizumab/LAG525 until recovery to grade $\leq$ 1 
 
• Restart spartalizumab/LAG525 at the same dose level
 

Grade (CTCAE v5)	Mandatory dose modification
Grade 3	
1st occurrence Interrupt spartalizumab/LAG525 until recovery to grade ≤ 1 or baseline
 
 
Restart spartalizumab/LAG525 at the same dose level
 
 
2nd occurrence Permanently discontinue spartalizumab/LAG525

Grade 4	Permanently discontinue spartalizumab/LAG525

**Table 6-6 Abnormal liver tests suspected to be related to spartalizumab or LAG525/spartalizumab**

Grade (CTCAE v5)	Mandatory dose modification
Grade 2	
Interrupt LAG525/spartalizumab until recovery to grade ≤ 1 or baseline
 
 
Restart spartalizumab/LAG525 at the same dose level
 
 
Patients with baseline grade 2 AST/ALT values may continue spartalizumab/LAG525

Grade 3 or 4	
Permanently discontinue spartalizumab/LAG525
 
Patients with baseline grade 2 AST/ALT values must permanently discontinue spartalizumab/LAG525 treatment if value increased to grade 3 with increase ≥ 2 × baseline

**Table 6-7 Rash/skin events suspected to be related to spartalizumab or spartalizumab/LAG525**

Grade (CTCAE v5)	Mandatory Dose Modifications
Grade 2 (e.g. rash 10 to 30% BSA, pruritus)	
If tolerable: continue spartalizumab/LAG525
 
If intolerable (or in case of bullous dermatitis, acute generalized exanthematous pustulosis or Drug Reaction with Eosinophilia and Systemic Symptoms): interrupt spartalizumab/LAG525 until tolerable or recovery to grade ≤ 1 or baseline
 
 
Restart spartalizumab/LAG525 at the same dose level
 

Grade 3 (e.g. rash > 30% BSA, pruritus) Other severe cutaneous adverse reactions Bullous dermatitis	
1st occurrence Interrupt spartalizumab/LAG525 until recovery to grade ≤ 1 or baseline
 
 
Restart spartalizumab/LAG525 treatment at the same dose level. For patients with severe cutaneous adverse reaction or bullous dermatitis, risk/benefit before resuming treatment should be carefully considered.
 
 
2nd occurrence Permanently discontinue spartalizumab/LAG525

Grade 4: Life-threatening	Permanently discontinue spartalizumab/LAG525
Stevens-Johnson syndrome (SJS), toxic epidermal necrolysis (TEN)	Permanently discontinue spartalizumab/LAG525

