## 6.3 Dose modifications

### 6.3.1 Mandatory dose modification and dose delay

For subjects who do not tolerate the protocol-specified dosing schedule, dose interruptions and/or reductions are mandated for treatment-related adverse events in order to manage subject safety and allow subjects to continue the study treatment.

Dose reductions are only allowed for capmatinib and ribociclib (refer to [Section 6.3.1.1](#)). Dose changes for spartalizumab, LAG525 and canakinumab are prohibited.

[Table 6-2](#) summarizes the mandatory dose modifications for specific treatment-related adverse events. If the specific adverse event is not listed, the guideline for ‘Other adverse events’ must be followed. AEs are to be graded according to NCI-CTCAE v5 ([ctep.cancer.gov](http://ctep.cancer.gov)) and all dose modifications should be based on the worst preceding toxicity. Deviations to mandatory dose interruptions and/or reductions are not allowed. Permanent treatment discontinuation is mandatory for specific events indicated as such in [Table 6-5](#) to [Table 6-37](#) and in [Section 6.3.1.5](#) or listed in [Section 7.1.5](#).

The investigator must follow the dose modifications for the study drug suspected to be related to the event:

- If the event is suspected to be related to spartalizumab, the investigator must follow the dose modifications specific for spartalizumab.
- If the event is suspected to be related to LAG525 or capmatinib or canakinumab or ribociclib, the investigator must follow the dose modifications specific for the suspected study drug.
- If it cannot be distinguished which of the study drugs within the combination is suspected to be related to the event, the investigator must follow the dose modifications specific to both study drugs within the combination.

Recommended management guidelines for suspected immune-related adverse events are provided in [Appendix 3](#) and can be amended according to the local or institutional guidelines.

Except for arm 1 where spartalizumab and LAG525 must be permanently discontinued at the same time, it is allowed for the other arms to discontinue one of the two study drugs within the combination. Permanent study treatment discontinuation is defined as the permanent discontinuation of both study drugs within the combination arm.

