**Table 6-9 Pneumonitis suspected to be related to spartalizumab or spartalizumab/LAG525**

Grade (CTCAE v5)	Mandatory dose modification
Grade 2	1st occurrence Interrupt spartalizumab/LAG525 until recovery to grade ≤ 1 or baseline 
 
Restart spartalizumab/LAG525 at the same dose level
 
 2nd occurrence Permanently discontinue spartalizumab/LAG525
Grade 3 or 4	Permanently discontinue spartalizumab/LAG525

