### **7.1.5 Discontinuation of study treatment**

Subjects who discontinue study treatment (i.e. when both investigational drugs are discontinued) at any time during the study for any reason should be scheduled for an End of Treatment (EoT) visit within 7 days after the discontinuation of the last study drug (i.e. within 7 days after the last dose of the last study drug or after the date when decision was made to permanently discontinue both study drugs/the last study drug), at which time all of the assessments for EoT will be performed as described in [Table 7-2](#).

At this EoT visit, all dispensed investigational drugs should be reconciled and the adverse event and concomitant medications recorded in the eCRF.

In addition to mandatory permanent discontinuation of study treatment in case of unacceptable toxicity (as described in [Section 6.3](#)), study treatment must also be discontinued under the following circumstances:

- Pregnancy of the female subject
- Use of a prohibited concomitant therapy (refer to [Section 6.4.3](#)).
- Any other protocol deviation that results in a significant risk to the subject's safety

The investigator may discontinue the study treatment for a given subject if he/she believes that continuation would be detrimental to the subject's well-being.

Subjects may voluntarily discontinue from the study treatment for any reason at any time. If a subject decides to discontinue from the study treatment, the investigator should make a reasonable effort (e.g. telephone, e-mail, letter) to understand the primary reason for this decision and record this information in the subject's chart and in the eCRF.

All subjects who discontinue study treatment should return for the safety assessments indicated in [Section 7.1.7](#), and if applicable, for the efficacy assessments indicated in [Section 7.1.8](#).

Subjects should NOT be considered withdrawn from the study, unless they state an intention to withdraw consent for all study assessments including follow up (see [Section 7.1.6](#)) or become lost to follow-up for any other reason (see [Section 7.1.10](#)).

The investigator must also contact the IRT to register the subject's discontinuation from study treatment. Site personnel will also have to record the End of Treatment in the Disposition page in the eCRF.

Crossover or re-randomization of subjects to other arms, including better performing arms, is not allowed.

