**Table 14-12 Recommended clinical management for suspected immune-related rash and other skin events**

Rash and other skin Events (NCI-CTCAE v5)	
Grade	Recommended management
Grade 1: rash covering < 10% Body Surface Area (BSA)	
 
• Initiate prophylactic and symptomatic treatment measures.
 
• Consider use of topical corticosteroids or urea containing creams in combination with oral antipruritics or moderate strength topical steroid (hydrocortisone 2.5% cream or fluticasone propionate 0.5% cream)
 
• Reassess after 2 weeks.
 

Grade 2: 10-30% of BSA	
 
• If tolerable, treat as per grade 1;
 
• If intolerable, initiate systemic steroids (e.g. oral prednisolone 0.5-1 mg/kg/d) and consider dose interruption until tolerable or recovery to grade ≤ 1 or baseline
 
• If symptoms persist or recur consider skin biopsy.
 

Grade 3: More than 30% of BSA	
 
• Obtain a skin biopsy and dermatology consult.
 
• Initiate systemic steroids with 1mg/kg/d of prednisone or equivalent.
 

Grade 4: Life-threatening	Same as grade 3; additional measures as per local institutional guidelines
Other skin events	
Stevens-Johnson syndrome, toxic epidermal necrolysis	
 
• Hospitalization and urgent dermatology consultation
 
• Institute supportive care immediately as per institutional guidelines
 

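### Table 6-7, read literally, lets dosing restart while bullous dermatitis, AGEP or DRESS is still grade 2, and its grade 2 and grade 3 rows overlap for bullous dermatitis

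*Protocol*

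**What the plan says.** Table 6-7 (Section 6.3.1.3.2) covers skin events suspected to be related to spartalizumab, alone or with LAG525. Its grade 2 row has two branches. A tolerable event continues on treatment. The second branch reads: "If intolerable (or in case of bullous dermatitis, acute generalized exanthematous pustulosis or Drug Reaction with Eosinophilia and Systemic Symptoms): interrupt spartalizumab/LAG525 until tolerable". The full release clause is "interrupt spartalizumab/LAG525 until tolerable or recovery to grade ≤ 1 or baseline", followed by a restart at the same dose.

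The next row is headed grade 3, with extensive rash as an example. Its label cell has two further lines with no grade attached: one for severe cutaneous reactions of other kinds, and one for bullous dermatitis. That row requires three things:
- a return to grade 1 or lower, or to baseline, before restart;
- careful weighing of risk and benefit before resuming in patients with a severe cutaneous reaction or bullous dermatitis;
- permanent discontinuation at the second occurrence.

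Section 6.3.1 makes the tables binding: "Deviations to mandatory dose interruptions and/or reductions are not allowed".

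**The concern.** The parenthesis in the grade 2 row can have only one purpose. An intolerable case of any of the three reactions is already caught by the word before it, so naming them must be meant to force a hold when they are tolerable. Yet the same branch lets tolerability end the hold. Its conditions are joined by 'or', and both triggers share one release.

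At stake is re-exposure to a checkpoint inhibitor during an active bullous, AGEP or DRESS reaction, which the parenthesis appears written to prevent. This is a subject-safety rule. It does not touch the response-rate endpoint, the interim decision rules or the sample size.

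**Working it through.** No arithmetic beyond a count applies. The check sets trigger against release, then looks for any other rule that would block an early restart.

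**1. Trigger and release in the grade 2 row, read literally**

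| Grade 2 event | Hold triggered? | Earliest release as written |
|---|---|---|
| Ordinary rash, tolerable | No | Not applicable |
| Ordinary rash, intolerable | Yes | When tolerable, even if still grade 2 |
| Named reaction, intolerable at onset | Yes | When tolerable, even if still grade 2 |
| Named reaction, tolerable at onset | Yes, through the parenthesis | Condition already met at onset |

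On this reading a named reaction is handled no more strictly than ordinary rash. In the last line the required hold has no length.

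**2. The neighbouring grade 2 holds**

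Grade 2 hold entries in Tables 6-5 to 6-12: diarrhea (6-5), liver tests (6-6), skin (6-7), creatinine (6-8), pneumonitis (6-9), and myasthenia gravis, acute pancreatitis and ocular events (6-12). Total: 1 + 1 + 1 + 1 + 1 + 3 = 8.
- Grade 1 or lower only: 1 (diarrhea).
- Grade 1 or lower, or baseline: 6. An example is the pneumonitis entry: "Interrupt spartalizumab/LAG525 until recovery to grade ≤ 1 or baseline".
- Tolerable as a further alternative: 1 (skin).

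Table 6-10 (endocrinopathies) releases on symptoms and hormone control but is not a grade 2 entry. The grade 2 entry in Table 6-11 contains no hold. Neither is counted.

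**3. Grade 2 row against the next row**

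If the two ungraded lines in the next row apply at any grade, grade 2 bullous dermatitis sits in both rows. One row releases it when tolerable. The other requires grade 1 or lower, or baseline, with a risk/benefit review and a second-occurrence stop. AGEP and DRESS may be in the same position if they count as severe cutaneous reactions, but the table does not define 'severe'. If instead those lines apply only at grade 3, the grade 2 row stands alone with its loose release.

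**4. Rules elsewhere that might block an early restart**
- Section 6.3.1.3 requires permanent discontinuation for "Persistent grade 2 or 3 adverse reactions (excluding endocrinopathies controlled with hormone replacement therapy) that do not recover to" grade 1 or lower within 12 weeks. Dosing is every 4 weeks, so an infusion can fall due before that limit.
- Section 6.3.1.3.1 says that once a dose of 10 mg or less "of prednisone (or equivalent) is achieved, spartalizumab or/and LAG525 can be restarted as indicated in" Tables 6-5 to 6-12. It delays restart only where systemic steroids were given, and then refers back to the same table. For grade 2 rash, Table 14-12 in Appendix 3 advises "If tolerable, treat as per grade 1", which means topical or antipruritic measures. An investigator who gives systemic steroids anyway does bring the taper condition into play.
- Section 7.1.5 states: "The investigator may discontinue the study treatment for a given subject if he/she believes that continuation would be detrimental". This is discretion, not a required hold.

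Each of these narrows the gap. None of them bars a restart at grade 2.

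**The case against.** The strongest reply is that the literal reading is not the natural one. It empties the parenthesis of meaning, so a sensible reader would pair 'tolerable' with 'intolerable' events and keep the recovery condition for the named reactions. Table 14-12 lends support, because there the same two-part release follows only an intolerable rash and the three reactions are not mentioned. This may well be what was intended. It is not what the row says, and a mandatory table should not depend on the reader supplying the pairing.

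A second reply is that the next row already gives the stricter rule, at least for bullous dermatitis. That is a fair reading of its ungraded lines, and it is why one should not conclude that the hold is void for all three reactions. But it leaves one event under two rows with different releases, which itself needs correcting.

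Third, a reader might infer that the protocol directs early re-dosing. It does not. The ban in Section 6.3.1 is on departing from required interruptions. The restart line fixes the dose level, and nothing obliges an investigator to resume as soon as the event is tolerable. Section 6.3.1.2 allows a hold of up to 12 weeks, and Section 6.3.3 requires at least weekly follow-up for the first 30 days after an interruption for an adverse event. All of this stands, and it limits the concern to what the text allows.

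**Conclusion.** The point holds as a drafting defect in a mandatory safety rule. Read literally, the grade 2 row allows restart while bullous dermatitis, AGEP or DRESS is still grade 2. It also gives a different release from the next row for at least grade 2 bullous dermatitis, if that row's ungraded lines apply at any grade. The conclusion rests on taking 'or' at face value and on finding no overriding rule elsewhere in the protocol.

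The defect is confined to one of eight grade 2 hold entries. New exposure is in arm 1A, planned at up to about 100 subjects (20 + up to 80, Section 4.1.2), because no randomized arm was enrolling at amendment 5 (Section 2.2). Subjects of the earlier arms still on treatment are also covered.

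It may be tempting to turn this into an expected number of affected subjects. The protocol gives no incidence for these reactions. The relevant cases would also have to be grade 2, tolerable while still grade 2, not on steroids above 10 mg, and due an infusion. No such number should be stated.

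**What to change.** Revise Table 6-7 at the next amendment:

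1. Keep the present release, with tolerability as one alternative, only for other intolerable grade 2 skin events such as rash or pruritus.
2. For grade 2 bullous dermatitis, AGEP or DRESS, tolerable or not, require interruption until grade 1 or lower, or baseline. Apply the same risk/benefit review before restart that the next row carries.
3. State which row governs each of the three reactions, and whether the ungraded lines in the grade 3 row apply at every grade.
4. State whether permanent discontinuation at a second occurrence applies when the event is grade 2.

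Splitting the grade 2 row alone is not enough, because bullous dermatitis would still appear in both rows. The cost is a wording change to two adjacent rows and a longer interruption for a few patients. Data collection and analysis are unchanged.
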